7.14 Baseline Descriptive Statistics.....	7-6
7.15 Device Issues	7-7

7.16 Planned Interim Analyses	7-7
7.17 Subgroup Analyses	7-7
7.18 Multiple Comparisons/Multiplicity	7-7
7.19 Additional Tabulations and Analyses	7-8
CHAPTER 8: DATA COLLECTION AND MONITORING	8-1
8.1 Case Report Forms and Device Data	8-1
8.2 Study Records Retention.....	8-1
8.3 Quality Assurance and Monitoring.....	8-1
8.4 Protocol Deviations.....	8-2
CHAPTER 9: ETHICS/PROTECTION OF HUMAN PARTICIPANTS	9-2
9.1 Ethical Standard	9-2
9.2 Institutional Review Boards.....	9-2
9.3 Informed Consent Process	9-2
9.3.1 Consent Procedures and Documentation	9-2
9.3.2 Participant and Data Confidentiality.....	9-2
9.3.3 Future Use of Stored Data.....	9-3
CHAPTER 10: REFERENCES.....	10-1

LIST OF ABBREVIATIONS

ABBREVIATION	DEFINITION
anti-VEGF	Anti-Vascular Endothelial Growth Factor
CI-DME	Central-Involved Diabetic Macular Edema
CRF	Case Report Form
CST	Central Subfield Thickness
DME	Diabetic Macular Edema
DR	Diabetic Retinopathy
DSMC	Data and Safety Monitoring Committee
E-ETDRS	Electronic-Early Treatment Diabetic Retinopathy Study
ETDRS	Early Treatment Diabetic Retinopathy Study
FDA	Food and Drug Administration
GCP	Good Clinical Practice
HbA1c	Hemoglobin A1c
ICH	International Conference on Harmonization
IDE	Investigational Device Exemption
IRB	Institutional Review Board
JCHR	Jaeb Center for Health Research
LED	Light Emitting Diode
OCT	Optical Coherence Tomography
PBM	Photobiomodulation
SAE	Serious Adverse Event
SD	Standard Deviation
UADE	Unanticipated Adverse Device Effect

[figure not shown]
PROTOCOL SUMMARY

SUBJECT AREA	DESCRIPTION
Title	A Pilot Study Evaluating Photobiomodulation Therapy for Diabetic Macular Edema (DME)
Précis	Randomized clinical trial evaluating the effect of photobiomodulation compared with sham on central subfield thickness (CST) in eyes with central-involved DME and good vision.
Objectives	
This study is being conducted to assess the effects of photobiomodulation on CST compared with sham in eyes with central-involved DME and good vision. Photobiomodulation is irradiation by light in the far-red (FR) to near-infrared (NIR) region of the spectrum (630-900 nm).
 
Furthermore, this pilot study is being conducted to determine whether the conduct of a pivotal trial has merit based on an anatomic outcome and provide information on outcome measures needed to design a pivotal trial.

Study Design	
Randomized, multi-center, sham-controlled clinical trial.
 
There are two phases of the study; the primary outcome will be evaluated at the end of phase 1 (first 4 to 8 months). At the primary outcome visit, participants originally assigned to active will end device use and participants originally assigned to sham will switch to active. The switch serves two purposes:
 
 1) to provide participants originally assigned to sham the opportunity to receive the active treatment and 2) to explore the post-outcome effects within treatment group. No statistical comparisons will be performed in Phase 2 to compare treatment groups. 
Note: This is not a crossover design.

Number of Sites	Approximately 40
Endpoint	
Primary Efficacy Outcome:
 
 • Mean change in CST from baseline to primary outcome visit

SUBJECT AREA	DESCRIPTION
	
Key Secondary Efficacy Outcomes: Treatment Group Comparisons
 
 • Mean change in retinal volume from baseline primary outcome visit • Percentage of eyes with CST below OCT machine- and gender-specific threshold for DME at primary outcome visit • Percentage of eyes receiving alternative treatment for DME by primary outcome visit • Percentage of eyes with a ≥ 5 letter loss in visual acuity • Patient compliance • Exploratory assessment of treatment effect after the device is stopped or started (see section 7.10 for more details)
Population	
Key Inclusion Criteria
 
 • Age ≥ 18 years • Type 1 or type 2 diabetes • At least one eye with each of the following: 
 • Best corrected E-ETDRS visual acuity letter score ≥ 79 (i.e., 20/25 or better) • Ophthalmoscopic evidence of central-involved DME in study eye confirmed by CST on spectral domain OCT: 
 ▪ Zeiss Cirrus: ≥ 290 μm in women, and ≥ 305 μm in men ▪ Heidelberg Spectralis: $\geq 305\mu\text{m}$ in women, and ≥ 320 μm in men 
Key Exclusion Criteria
 
 • No history of prior laser, surgical, intravitreous, or peribulbar treatment for DME or DR in the study eye within the prior 12 months 
 ○ If more than 12 months ago, no more than 4 prior intraocular injections ○ Enrollment will be limited to a maximum of 15% of the planned sample size with any history of anti-VEGF treatment and a maximum of 15% with any history of PRP.

SUBJECT AREA	DESCRIPTION
Sample Size	134
Treatment Groups	Random assignment (1:1) to photobiomodulation (PBM) or sham
Participant Duration	The trial will last up to 12 months for each participant (primary outcome at 4 to 8 months and final visit at 8 to 12 months)
Protocol Overview	
 1. Informed consent will be obtained. 2. Study eligibility will be assessed. 3. Prior to randomization, the participant's willingness to proceed into the randomized trial will be confirmed. 4. Eligible eyes (one per participant) will be randomly assigned to photobiomodulation or sham. If a participant has two eligible eyes, the eye with the greatest CST will be selected as the study eye and the non-study eye will be followed to evaluate any potential contralateral effect. 5. Training for at-home use will be performed with the randomized device on the day of randomization. 6. A follow-up phone call is performed at 1 week. 7. Participants will return for a follow-up visit every month for the first ~4 months and then every 2 months for 4 months after the primary outcome. The primary outcome assessment will be at ~4 months. 8. Following the primary outcome assessment, participants in the active group will end device use and participants in the sham group will be given the option to switch to the active treatment for the next 4 months. Participants in both groups who do not continue treatment will be given the option to end study participation after the primary outcome visit. A summary of treatment procedures is included below.

SCHEMATIC OF STUDY DESIGN

SCHEDULE OF STUDY VISITS AND PROCEDURES

	Baseline	1-week Phone Call	Interim Visits (1, 2, 3, 6M)	Primary Outcome and Final Visits	DME Tx Initiation Visit*
Device Training	X				
Randomization	X				
E-ETDRS Best Corrected Visual Acuity [†]	X		X	X	X [‡]
Spectral Domain OCT [§]	X		X	X	X
OCTA [¶]	X			X	
Eye Exam [¶]	X		If Needed	X	X
Blood Pressure	X				
HbA1c ^{**}	X				
Compliance Assessment		X	X	X	

Notes

Testing is only required for the study eye unless otherwise specified below.

*Alternative DME treatment (e.g. anti-VEGF) should not be performed unless protocol criteria are met. If alternative DME treatment is planned at an unscheduled visit, study testing must be completed prior to treatment.

[†]Visual acuity performed on both eyes at each visit, including protocol refraction on both eyes at baseline, 4-month, and final visit, and on the study eye only at all other protocol visits.

[‡]Usual care vision may be used if eye has already been dilated when treatment is planned.

[§]OCT in both eyes at all visits; OCT may be obtained with Zeiss Cirrus or Heidelberg Spectralis OCT machines only.

[¶]Baseline and 4-Month visit only at select sites with OCTA capabilities

[¶]Both eyes at baseline visit, study eye only at 4 month and 8-month visits. Ocular exam at interim visits is at investigator discretion. In general, an ocular exam should be completed if the OCT and/or visual acuity have worsened since baseline.

^{**}Does not need to be repeated if HbA1c available from within the prior 3 months; if not available, can be performed within 3 weeks after randomization.

CHAPTER 1: INTRODUCTION

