333 prior to randomization or plans to do so in the next 4 months.

334 8. Participation in an investigational trial that involved treatment within 30 days of randomization
335 with any drug/device that has not received regulatory approval for the indication being studied.

336 • *Note: study participants cannot participate in another investigational trial that involves
337 treatment with an investigational drug or device while participating in the study.*

338 9. Blood pressure > 180/110 (systolic above 180 or diastolic above 110).

339 • *If blood pressure is brought below 180/110 by anti-hypertensive treatment, individual can
340 become eligible.*

341 10. Systemic anti-VEGF or pro-VEGF treatment within 4 months prior to randomization.

342 • *These drugs should not be used during the study.*

343 11. For women of child-bearing potential: pregnant or intending to become pregnant within the
344 next 8 months.

345 • *Women who are potential study participants should be questioned about the potential for
346 pregnancy. Investigator judgment is used to determine when a pregnancy test is needed.*

347 12. Individual is expecting to move out of the area during the 8 months of the study.

348 **2.2.2 Study Eye Criteria**

349 To be eligible, the study participant must have at least one eye meeting all of the inclusion criteria
350 and none of the exclusion criteria listed below.

351 A participant can have only one study eye. If a participant has two eligible eyes, the eye with the
352 greatest central subfield will be selected as the study eye and the non-study eye will be followed
353 to evaluate any potential contralateral effect.

356 The eligibility criteria for a study eye are as follows:

357 Inclusion

358 a. Best corrected E-ETDRS visual acuity letter score ≥ 79 (i.e., 20/25 or better)

359 b. Ophthalmoscopic evidence of central-involved DME, confirmed by CST on spectral domain
360 OCT:

361 ■ Zeiss Cirrus: $\geq 290\mu\text{m}$ in women, and $\geq 305\mu\text{m}$ in men
362 ■ Heidelberg Spectralis: $\geq 305\mu\text{m}$ in women, and $\geq 320\mu\text{m}$ in men
363 c. Media clarity, pupillary dilation, and study participant cooperation sufficient for adequate
364 OCT.

365

366 Exclusion

367 d. Macular edema is considered to be due to a cause other than DME.
368 • *An eye should not be considered eligible if: (1) the macular edema is considered to be
369 related to ocular surgery such as cataract extraction or (2) clinical exam and/or

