479 8 months post-randomization (see visit windows below). If the visit is not completed by 8 months,
480 the participant will be instructed to discontinue device use, return the study device as soon as they
481 are able, and study participation will be ended.

482

483 **3.1.3 Post-Outcome Phase**

484 At the 4-month visit, all participants will be unmasked to their treatment group assignment.

485

486 Participants originally assigned to Sham who have not already received alternative DME treatment
487 (see section 3.6) will return the original device and have the option to receive the active treatment
488 group device for the next 4 months.

489

490 Participants originally assigned to Active who have not received alternative treatment will return
491 the original device and have the option to complete the remaining follow-up visits without device
492 use.

493

494 **3.1.4 Device Training**

495 On the day of randomization, a device will be provided to the participant according to their
496 randomized assignment. In order for investigators to remain masked, clinical site coordinators
497 will instruct study participants regarding the proper use of the device. The eyelid must be closed
498 for the duration of the treatment. The participant must turn the device on and it will stop
499 automatically. The study participant will be asked to demonstrate proper use in the office, which
500 will be considered the initial treatment. The participant will be instructed to complete the second
501 treatment that day before bed.

502

503 **3.2 Study Visits and Phone Contacts**

504 A phone call is completed by site personnel within approximately one week of randomization (5
505 to 14 days) to emphasize compliance with device use and answer any questions.

506

507 Scheduled follow-up visits will occur at the following times (time from randomization unless
508 otherwise noted):

509

Visit	Target Date	Target Window (around Target Date)	Allowable Window (around Target Date)
1 Month	4 weeks	± 1 week	± 2 weeks
2 Month	8 weeks	± 1 week	± 2 weeks
3 Month	12 weeks	± 1 week	± 2 weeks
4 Month/Primary Outcome Visit*	16 weeks	± 2 weeks	-4 weeks/+16 weeks
~6 Month/2-month post outcome	8 weeks after 4- Month visit	± 2 weeks	± 4 weeks
~8 Month/4-month post outcome	16 weeks after 4- Month visit	± 2 weeks	-8 weeks/+12 weeks

510

*Key visit

511

512 The goal will be for all participants to complete all scheduled visits. However, participants who

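### The visit windows allow participation up to week 60, beyond the stated 12 months, and SAP Table 3 counts the post-outcome windows from randomisation although their targets count from the primary visit

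*Protocol*

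**What the plan says.** **Duration.** The Participant Duration row of the Protocol Summary reads "The trial will last up to 12 months for each participant" and adds "primary outcome at 4 to 8 months and final visit at 8 to 12 months".

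**Visit windows.** Protocol 3.2 counts visits from randomisation unless it says otherwise. The primary visit has a target of 16 weeks and an allowable window of minus "4 weeks/+16 weeks". The final visit has a target of 16 weeks after the 4-month visit and an allowable window of minus "8 weeks/+12 weeks". The 2-month post-outcome visit has a target of 8 weeks after the 4-month visit, plus or minus 4 weeks. Protocol 3.1.2 repeats the late limit of the primary visit in words, as up to "8 months post-randomization (see visit windows below"), and ends participation if that visit is missed. No comparable limit from randomisation is given for the final visit.

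**Eligibility.** Exclusion 12 in Protocol 2.2.1 reads "Individual is expecting to move out of the area during the 8 months of the study". Exclusion 11 asks about intended pregnancy over the same number of months.

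**Analysis windows.** SAP 8.2, Table 3, gives the post-outcome targets as 8 and 16 weeks after the 4-month visit. Its windows are days 140 to 280 for the 2-month post-outcome visit and days 168 to 336 for the final visit.

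**The concern.** The summary and the visit table cannot both be right about how long a participant may be followed. The summary's range for the primary visit uses the late end of that visit's allowable window; its range for the final visit does not.

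The SAP mismatch has a practical consequence. A target that moves with the primary visit, paired with a window that does not, can reject a visit made when the protocol asked for it. For the Phase 2 thickness and volume outcomes, SAP 3.0 does not impute for participants who miss the final visit without having had alternative treatment. If Table 3 is applied literally, a measured value would therefore be dropped. The participants at risk are those whose primary visit was late, so the loss would not be a random one.

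**Working it through.** **Inputs.** Targets and allowable windows from Protocol 3.2; stated duration from the Protocol Summary; analysis windows from SAP Table 3. A calendar month is taken as 30.4375 days, so 12 months = 52.2 weeks. The protocol itself uses four weeks per month (its 4-month visit is at week 16).

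**1. Where 12 months comes from.** Latest primary visit + on-target final visit = (16 + 16) + 16 = 48 weeks, which is 48 / 4 = 12 four-week months. The other combinations tried do not give 12:
- on-time primary, latest final: 16 + 28 = 44 weeks
- latest primary, end of the final visit's ±2-week target window: 32 + 18 = 50 weeks.

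**2. Range the visit table allows.**
- Primary visit: 16 − 4 = 12 to 16 + 16 = 32 weeks.
- Final visit after it: 16 − 8 = 8 to 16 + 12 = 28 weeks.
- Earliest final visit: 12 + 8 = 20 weeks = day 140 = 4.6 calendar months (stated: 8).
- Latest final visit: 32 + 28 = 60 weeks = day 420 = 13.8 calendar months, or 15 four-week months (stated: 12).

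The excess is 60 − 52.2 = about 8 weeks in calendar months, or 60 − 48 = 12 weeks in four-week months. A final visit at the end of its window passes 52.2 weeks once the primary visit is later than 52.2 − 28 = about week 24.

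**3. Time origin of the SAP windows.** Table 3 does not state it, but it can only be randomisation. Counted from the primary visit, an on-target final visit is day 112 and an on-target 2-month visit is day 56; both lie before their windows open (168 and 140).

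**4. Which allowed final visits the SAP window accepts.** With the primary visit at week p, the protocol allows weeks p + 8 to p + 28; the SAP accepts weeks 24 to 48.

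| Primary visit (week) | Final visit allowed (days) | On target (day) | Outside days 168–336 |
|---|---|---|---|
| 12 | 140–280 | 196 | 140–167 |
| 16 | 168–308 | 224 | none |
| 20 | 196–336 | 252 | none |
| 24 | 224–364 | 280 | 337–364 |
| 32 | 280–420 | 336 | 337–420 |

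- Nothing is lost when 16 ≤ p ≤ 20.
- Late losses need p + 28 > 48, so p > 20.
- Early losses need p < 16 and a final visit before week 24. At p = 12 that means more than 4 weeks ahead of target, and further ahead as p nears 16.
- For a final visit inside the protocol's own ±2-week target window, late loss needs p + 18 > 48, so p > 30. At p = 32 a visit two weeks past target is day 350, against a limit of 336.

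**5. The 2-month post-outcome visit.** Allowed: 12 + 4 = 16 to 32 + 12 = 44 weeks. SAP: 140 / 7 = 20 to 280 / 7 = 40 weeks. The mismatch is the same, though SAP 3.0 lists no outcome read at this visit.

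**6. Primary visit.** Weeks 12 to 32 = days 84 to 224 in both documents. They agree.

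**The case against.** The best defence is that 12 months is a planned duration: the latest primary visit plus a 4-month second phase. On the protocol's month that is exactly 12, and allowances for lateness need not be counted. This explains the figure but does not fully rescue it. The same sentence does count the primary visit's late allowance, and it says up to.

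It is also fair to say that most participants would never meet the SAP mismatch. A primary visit at weeks 16 to 20 costs nothing, and an on-target final visit is always accepted, if only on the last day. Phase 2 has no between-group comparison and its within-group tests are exploratory. That stands, and it limits the importance of the point.

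Two stronger readings are tempting, and the documents support neither.

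- A reader might count 28 + 84 = 112 of the 281 permitted days (140 to 420) as outside the SAP window and infer that a similar share of final visits is lost. That would weight every day equally, whereas most of those days need an off-schedule primary visit and an early or late final visit as well. It is not a share of participants.
- A reader might call the 8-month pregnancy horizon an error. It is a screening question about intention, and it covers Phase 1 to its latest limit of week 32. Protocol 5.3 deals with a pregnancy that does occur by stopping the device at once. Nothing requires the horizon to span the longest possible follow-up. Exclusion 12 differs only in that it names 8 months as the length of the study.

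**Conclusion.** The inconsistency is real and minor. The allowed final visit runs from week 20 to week 60; the stated 12 months is exceeded by 8 to 12 weeks, depending on how a month is counted. Reaching week 60 needs both visits at the end of their windows.

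In SAP Table 3, final visits that the protocol allows can fall outside the window when the primary visit is later than week 20, or earlier than week 16 with a markedly early final visit. A final visit inside the protocol's target window is lost only when the primary visit is later than week 30. The number of participants affected cannot be computed, because the documents give no distribution of visit times.

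The conclusion assumes that the SAP days count from randomisation (step 3) and that a visit outside its window is treated as missing. The Phase 2 thickness and volume summaries would lose the value. The Phase 2 adherence analyses in SAP 4.0, which handle missing data as in Phase 1, would impute it. The primary analysis, the Phase 1 secondary comparisons and the sample size are unaffected.

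**What to change.** 1. **SAP Table 3.** Count both post-outcome windows from the actual primary visit, to match Protocol 3.2: 28 to 84 days after it for the 2-month visit (8 ± 4 weeks) and 56 to 196 days after it for the final visit (16 − 8 to 16 + 12 weeks). State the time origin in the table. These windows overlap on days 56 to 84, as the present ones do on days 168 to 280. SAP 8.2 gives overlaps to the key visit, so add a rule that keeps an on-target 2-month visit (day 56) from being taken as the final visit.
2. **Protocol Summary.** Either state the maximum as 60 weeks (about 14 months), with the final visit from week 20, or keep the 12 months and cap the final visit from randomisation in Protocol 3.2. A cap at 48 weeks leaves no late allowance after a week-32 primary visit (48 − 32 = 16 weeks); a cap at 52 weeks leaves 4 weeks.
3. **Exclusion 12.** Replace the 8-month study length with wording that matches the chosen maximum. If 8 months is the intended screening horizon, state it as a horizon and not as the length of the study. Exclusion 11 can stay.

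The cost is a few lines of protocol and SAP text. No analysis method, error rate or sample size changes. Stating 60 weeks lengthens the declared participation; a cap forgoes some late final visits.

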1.1 Introduction

1.1.1 Diabetic Macular Edema and Public Health Impact

In the United States, an estimated 30.2 million adults have diabetes mellitus (23 million diagnosed, 7.2 undiagnosed).¹ From 2005 to 2008 diabetes was reported to be the leading cause of new cases of blindness among adults in the United States.² Nearly 8 million people over the age of 40 in the United States are estimated to have diabetic retinopathy (DR).³ Diabetic macular edema (DME), a consequence of retinopathy, is the most common among the conditions that contribute to vision loss in persons with diabetes; nearly half of all people with DR will develop DME.⁴

1.1.2 Current Treatment for DME

DME is a manifestation of diabetic retinopathy that produces loss of central vision. Although prior studies have clearly demonstrated that intravitreous anti-VEGF is the most effective monotherapy for central-involved DME (CI-DME) and decreased vision^{10,10-13,11-13}, anti-VEGF treatment does have disadvantages including the need for recurrent injections as often as once a month and a small risk of serious complications, such as endophthalmitis. Moreover, evidence indicates that DME is not satisfactorily resolved in all patients. Thus, there is an ongoing need to identify novel therapies that are both effective for DME treatment and that also avoid the potential adverse events or costs associated with current ocular interventions.

Furthermore, baseline cohort characteristics from the Early Treatment Diabetic Retinopathy Study (ETDRS) suggest that a substantial percentage of eyes with CI-DME may retain good vision. At baseline in the ETDRS, of all eyes in the focal laser and observation group, center involved macular edema on fundus photographs was present in approximately 42% of eyes. Of these eyes, 64% had baseline visual acuity \geq 79 letters (approximately 20/25 or better). (Personal communication [name]) Several questions remain regarding treatment of the cohort of eyes with CI-DME and good visual acuity. In a review of early studies concerning the natural history of DME, Ferris and Patz found that 53% of 135 eyes with DME lost two or more lines of visual acuity over a two year period.¹⁴ Furthermore, without intervention, 33% of 221 eyes included in the Early Treatment Diabetic Retinopathy Study (ETDRS) with central-involved DME experienced “moderate visual loss” (defined as a 15 or more letter score decrease in visual acuity) over a three year period.¹⁵ Thus, there may be rationale for initiating treatment for CI-DME as soon as DME meets clinically significant criteria but before vision begins to decline.¹⁶ The advent of OCT now allows us to determine the presence of and monitor changes in CI-DME with increased sensitivity over the fundus photographic grading method used in the ETDRS. Given the potentially large numbers of patients with CI-DME and good vision, and the current lack of guidance regarding best treatment practice for this group of eyes, evaluation of a low-risk, non-invasive treatment alternative to anti-VEGF in this cohort is warranted.

While focal photocoagulation (direct treatment to microaneurysms and grid treatment to diffuse edema) was shown in the ETDRS to reduce the risk of moderate visual loss from DME by approximately 50%,¹⁷ this direct treatment with high-intensity light also causes retinal scarring and loss of photoreceptors.¹⁸ More recent studies, however, have found that specific wavelengths of *low-intensity* light that are absorbed by cellular photoreceptor molecules result in activation of signaling pathways that cause biological changes on a cellular level without the destructive properties found in high-intensity lasers.

44 **1.1.3 Photobiomodulation**

45 Irradiation by light in the far-red (FR) to near-infrared (NIR) region of the spectrum (630-900 nm)
46 collectively termed “photobiomodulation” (PBM) can restore the function of damaged
47 mitochondria, upregulate the production of cytoprotective factors, decrease inflammation and
48 prevent cell death. PBM has been applied clinically in the treatment of soft tissue injuries and
49 acceleration of wound healing for more than 50 years. Recent studies have demonstrated that
50 FR/NIR photons penetrate diseased tissues including the retina. The therapeutic effects of PBM
51 have been hypothesized to result from intracellular signaling pathways triggered when FR/NIR
52 photons are absorbed by cellular photo-acceptor molecules, such as mitochondrial cytochrome c
53 oxidase, culminating in improved mitochondrial energy metabolism, decreased inflammation and
54 cell survival. Investigations in animal models of retinal injury and retinal disease including diabetic
55 retinopathy, age-related macular degeneration and retinitis pigmentosa have demonstrated the
56 PBM attenuates cell death, protects retinal function and exerts anti-inflammatory actions. An
57 increasing number of small clinical studies have documented therapeutic efficacy of PBM in AMD
58 and diabetic retinopathy. In addition to wound healing, FR to NIR light (630-1000nm) has now
59 been reported to be beneficial in a variety of conditions including recovery from ischemic injury
60 to the heart,¹⁹ treatment of gingival incisions,²⁰ peripheral nerve repair after trauma,^{21, 22} and
61 treatment of acute soft tissue injuries.²³ The FDA approved the use of low-light therapy for carpal
62 tunnel syndrome in 2003.²⁴ Far-red light likewise has been found to inhibit production of the
63 proinflammatory cytokines, IFN- γ and TNF- α , and to upregulate anti-inflammatory cytokines, IL-
64 4 and IL-10 in experimental autoimmune encephalomyelitis.²⁵

65 FR/NIR light (commonly 660-670 nm) has also has beneficial effects on the retina. Eells *et al.*,²⁶
66 reported the first direct link between the actions of far-red light on mitochondrial bioenergetics *in*
67 *vitro* and retinoprotection *in vivo* using an established model of retinal mitochondrial toxicity,
68 methanol intoxication. Accumulation of formic acid generated from methanol oxidation in the
69 course of methanol poisoning produces toxic injury to the retina and optic nerve, resulting in
70 blindness¹⁴ An acute toxic exposure to methanol results in an increase in tissue formic acid
71 concentrations, metabolic acidosis and visual toxicity within 72 hours of ingestion.²⁷ Formic acid
72 is the mitotoxic metabolite in methanol intoxication. Formic acid inhibits cytochrome c oxidase
73 by reversibly binding to the same site as cyanide and azide¹⁴. These studies demonstrated that three
74 brief 670 nm LED treatments (160 sec at 25 mW/cm² producing a fluence 4 J/cm² at the surface
75 of the eye) (Spectralife, Quantum Devices Inc., Barneveld WI) treatments delivered at 5, 25, and
76 50 h of methanol intoxication, attenuated the retinotoxic effects of methanol-derived formate. The
77 authors documented a significant protection against formate-induced retinal dysfunction during
78 the course of intoxication. 670 nm light also protected the retina from the histopathologic changes
79 induced by methanol-derived formate. These findings provided the first link between the actions
80 of FR light on mitochondrial oxidative metabolism *in vitro* and retinoprotection *in vivo*. Moreover,
81 they were the first studies to suggest that FR PBM had therapeutic potential for the treatment of
82 retinal injury and disease. Subsequent studies have documented retinoprotection in rodent models
83 of high intensity light damage, retinitis pigmentosa, diabetic retinopathy and age-related macular
84 degeneration.²⁸

85 **1.1.4 Relevant Prior Studies of PBM (670nm)**

86 **1.1.4.1 Animal Studies**

87 Diabetes results in increases in oxidative stress in the retina, and increased expression of pro-
88 inflammatory proteins. Oxidative stress and proinflammatory proteins in the retina are important

89 in diabetes, because previous studies have shown that vascular lesions of early diabetic retinopathy
 90 are significantly inhibited in animal models if oxidative stress and inflammatory changes are
 91 inhibited.^{29,30} Consistent with this, diabetic-like concentrations of glucose (20-30 mM) likewise
 92 result in increased superoxide production, inflammatory biomarker expression, and cell death in
 93 cultured retinal cells. PBM was able to inhibit these abnormalities in vitro.

94 Tang et al.³¹ investigated the therapeutic efficacy of 670-nm PBM in albino rats (Lewis) which
 95 had been made diabetic with streptozotocin. With daily 4-minute PBM treatment (6 J/cm²) for 10
 96 weeks from the onset of diabetes, there was significant inhibition in the diabetes-induced death
 97 (apoptosis) of retinal ganglion cells (Figure 1), as well as a 50% improvement of the ERG
 98 amplitude (photopic b wave responses) (Figure 2) (both $P < 0.01$), indicating both structural and
 99 functional benefit of PBM in diabetes.³¹

[figure not shown]

Fig 1.

[figure not shown]

Fig 2.

100

101

102 PBM also inhibited the diabetes-induced generation of superoxide (Fig 3), induction of markers of
 103 inflammation (leukostasis, expression of the Inducible isoform of Nitric Oxide Synthase (iNOS))
 104 (Fig 4), and preserved MnSOD expression (an enzyme that helps protect against superoxide

105 damage; not shown) in vivo.³¹ Daily application of the light therapy was more efficacious than
 106 every other day administration.

Fig 3. Diabetes (2 months) increased superoxide production by retina, and this increase was inhibited by 4 minutes per day PBM. Administration of PBM either daily or only three times per week both significantly inhibited the superoxide generation, but daily therapy was more effective.

107

[figure not shown]

Fig 3.

108 While diabetes significantly increased both leukostasis and expression of ICAM-1, they showed
 109 that PBM essentially prevented both of these abnormalities (Fig 4A and 4B, respectively).³¹ These
 110 data indicate that the PBM inhibited at least some key aspects of the diabetes-induced local
 111 oxidative stress and inflammation in the retina.

[figure not shown]

Fig 4.

112

113 More recently, Saliba, et al.³² further tested whether the beneficial effects of PBM for retinal
 114 disease seen in the aforementioned studies would extend to (i) other species, (ii) in the presence of
 115 heavy pigmentation (C57Bl/6J mice), and (iii) as an intervention therapy after diabetes onset.
 116 PBM was applied to pigmented mice for 4 min/day for 10 weeks, starting 4 weeks after the
 117 induction of diabetes. The results indicated that PBM significantly reversed the diabetes-induced
 118 increase in retinal superoxide and leukostasis (Fig 5a and 5b, respectively), and significantly
 119 inhibited also the diabetes-induced increase in retinal ICAM-1 expression (not shown). The
 120 intervention with PBM also significantly inhibited the development of a diabetes-induced defect
 121 in visual function as measured by spatial frequency threshold ($p < 0.0001$).

[figure not shown]

Fig 5.

122

123

124 Interestingly, at least some of the beneficial effects of PBM were demonstrated also in a second
 125 group of mice in which the PBM was unable to directly shine on the eyes, as a result of a lead
 126 shield covering the head during the PBM to prevent direct irradiation to the eye.

127

128 In an effort to determine which retinal cell-types the PBM was affecting, light-induced movement
 129 of ions into retinal cells was assessed in diabetic and nondiabetic mice using Manganese-enhanced
 130 MRI. Manganese is used as a surrogate of calcium for these studies, since manganese is known to
 131 be transported into cells via calcium channels, and unlike calcium, it can be detected by MRI.
 132 These studies demonstrated that diabetes reduced transport of manganese (and presumably
 133 calcium) into photoreceptor cells and essentially all other secondary neurons, and PBM treatment
 134 largely inhibited this except in the presumptive rod inner segment layer.

[figure not shown]

Fig 6.

135

136 Most importantly, long-term (8 months) daily application of PBM (670 nm, 4 min/day) recently
 137 has been shown to inhibit the development of clinically meaningful lesions of early DR in mice.³³
 138 PBM was administered daily from the onset of diabetes, and the daily light therapy significantly
 139 inhibited the diabetes-induced leakage in each of the 3 layers of the retinal microvasculature (Fig
 140 7) and degeneration of retinal capillaries (Fig 8), and also significantly inhibited the diabetes-
 141 induced reduction in visual function (visual acuity [spatial frequency threshold] and contrast
 142 sensitivity; not shown).

143

[figure not shown]

Fig 7.

[figure not shown]
144
145

Fig 8.

146
147
148

149 These animal studies provide evidence of beneficial actions of PBM on numerous key early
 150 changes of diabetic retinopathy, and on clinically meaningful morphologic lesions of the
 151 retinopathy.

152 **1.1.4.2 Clinical Studies in Diabetic Retinopathy**

153 Following the promising results seen in the above-mentioned animal studies, PBM has now been
 154 evaluated in two small clinical studies of treatment for diabetic macular edema. Tang, et al.
 155 reported the results of a non-randomized, consecutive case series that evaluated PBM for non-
 156 center involving DME involving four patients with bilateral edema who were treated in one eye
 157 and the fellow eye served as the untreated control. After treatment for 160s per day (9 J/cm²) for
 158 2 to 9 months, thickened areas on spectral domain OCT were reduced by a mean of 20% (±11.7%)
 159 in the treated eyes and mean change in the untreated eyes was -3% (±8%).³⁴ Percent area of
 160 thickened retina across the macular region was determined manually on the Spectralis-generated
 161 color thickness map (Fig 9).
 162

Effect on Non ciDME using 3 min/day of 670nm Light

[figure not shown]

Fig 9.

163
164 Eells et al conducted a randomized prospective study in 10 patients with treatment resistant DME,
165 randomized to either standard treatment with continued anti-VEGF alone or anti-VEGF plus PBM.
166 Light treatment was administered at a dose of 4.5 J/cm^2 three consecutive days per week for 8
167 weeks using a 670 nm LED Array (WARP-10, Quantum Devices, Inc., Barneveld, WI) positioned
168 2.5 cm from the closed treatment eye. Functional and anatomic assessments were made at baseline,
169 8 weeks and 24 weeks. The authors reported a change from baseline at 24 weeks in central retinal
170 thickness of -24 ± 5 microns in the PBM group (N=6) and $+120 \pm 97$ microns in the standard
171 treatment group (N=4). Visual acuity also improved by an average of 6 ± 5 letters in the PBM
172 group, compared with a 3 ± 4 letter decrease in VA in the standard treated group. No adverse effects
173 attributable to 670 nm PBM were noted by the patients or study investigators during the study
174 period. Although the sample size is small, the findings show a reduction in DME and an
175 improvement in VA following NIR-PBM. Results support the application of NIR-PBM for the
176 treatment of DME in eyes refractory to anti-VEGF treatments. (ARVO 2017 presentation)

